### **3.2.2 Screening**

A sequential site specific volunteer number will be assigned to each subject for identification purposes. Informed consent will then be obtained. Then the subject will be screened to assess eligibility for the study.

A screening log will be maintained by the site that records all subjects for whom consent was obtained and who entered the screening process. The screening log will record the sex, age and racial or ethnic identity of the candidate subjects. Abnormal results and findings resulting in ineligibility will be discussed with the subject, who will be referred for follow-up care with their healthcare provider if necessary. Only screening information from consented, eligible and dosed individuals will be entered into the study database. Eligibility for entry into the study will be based on the inclusion and exclusion criteria described below. The investigator must document confirmation of eligibility prior to randomization. The serum chemistry labs for screening visit that determine eligibility are: AST, ALT, ALP and creatinine. These are a subset of the larger clinical safety laboratory analytes. Other serum chemistry values (total bilirubin, BUN etc.) that are collected for safety monitoring (Table 3.1-1) will be collected for Study Day 0 baseline values but are not part of the inclusion/exclusion criteria as such.

### **3.2.3 Inclusion Criteria**

**Subjects must meet all of the following criteria at the time of subject ID assignment:**

1. Male or female subjects between 18 and 50 years of age, inclusive
2. Body mass index between 18 and 30 kg/m^2, inclusive
3. Female subjects physically capable of pregnancy (i.e., not sterilized and still menstruating or within 1 year of the last menses if menopausal) must:
  - a. Agree to avoid pregnancy from 28 days prior to Study Day 0 through the duration of the study.

- b. If in a sexual relationship with a man, use an acceptable method of avoiding pregnancy during this period. Acceptable methods of avoiding pregnancy include: the use of at least two forms of contraception, including use by a partner of a barrier method (e.g., male condom with intravaginal spermicide) as one form of contraception.
4. Women of childbearing potential must have a negative serum pregnancy test within 48 hours preceding receipt of the first dose.
5. Can understand and sign the informed consent document, can communicate with the investigator and provide updated contact information as needed for the duration of the study, has no current plans to move from the study area for the duration of the study, and can understand and comply with the requirements of the protocol.

### **3.2.4 Exclusion Criteria**

**Subjects must have none of the following at the time of subject ID assignment:**

1. Oral temperature  $\geq 37.5^{\circ}\text{C}$  at screening
2. Complete blood count (CBC) and platelet count abnormal values ( $>5\%$  above the upper limit of normal [ULN] or  $>5\%$  below the lower limit of normal [LLN] per local laboratory parameters) at screening with exception of absolute lymphocyte count.
3. Abnormally elevated aspartate aminotransferase (AST), alanine aminotransferase (ALT), total bilirubin, alkaline phosphatase (ALP), or creatinine (Cr) values at screening (however a single test AST, ALT or ALP may be  $>10\%$  above the ULN per local laboratory parameters)
4. Abnormal PT (INR) PTT
5. Abnormal screening urinalysis result that is, per the investigator, clinically significant, or a screening urine dipstick result of  $\geq 2+$  protein
6. Positive screening urine test for illicit drugs (opiates, cocaine, amphetamines, methamphetamines, barbiturates, benzodiazepines, tetrahydrocannabinol, PCP, MDMA, and methadone)
7. History or evidence of autoimmune disease
8. History or evidence of any past, present, or future possible immunodeficiency state, including laboratory evidence of human immunodeficiency virus (HIV) 1 or 2 infection
9. History or evidence of chronic hepatitis

10. History or evidence of rabies infection
11. History or evidence of any other acute or chronic disease that, in the opinion of the investigator, may interfere with the evaluation of the safety or immunogenicity of the drug or compromise the safety of the subject; for example a clinically relevant history of respiratory, thyroid, gastrointestinal, renal, hepatic, hematological, lymphatic, oncologic, cardiovascular, psychiatric, neurological, musculoskeletal, genitourinary, infective, inflammatory, immunological, dermatological or connective tissue disease
12. History or evidence of allergic disease or reaction, including adverse responses to therapeutic monoclonal antibodies that, in the opinion of the investigator, may compromise the safety of the subject
13. History of non-compliance that, in the opinion of the investigator, will make it unlikely that the subject will comply with the protocol
14. Previous exposure to rabies vaccine
15. Receipt of an immunoglobulin or blood product within 90 days prior to Study Day 0
16. Receipt of immunosuppressive medications other than inhaled or topical immunosuppressant drugs within 45 days prior to Study Day 0
17. Body weight greater than 90 kg.
18. History or evidence of IgA deficiency

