**Table 3.1-1 Summary Schedule of Subject Treatment and Evaluations**

Study Visit Day →	Screen	-2	0	1	3	7	14	28	35	42	84	112
Visit Window d		0	0	0	0	1	1	3	4	4	8	11
Written informed consent	X											
Eligibility criteria verification	X											
Medical history	X											
Physical examination	X											
ECG e	X		X	X	X	X	X	X				X
Urine toxicology screen	X											
Urine βHCG (all females) e	X				X	X	X	X				X
Serum βHCG (all females) a		5										
Serum Hepatitis B, C tests	3											
Serum HIV-1,2 tests	3											
Rabies Vaccine administration			X		X	X	X	X				
Study Drug Administration			X									
Urinalysis e	X		X	X	X	X	X	X	X	X		X
Serum Anti-rabies activity e			10	10	10	10	10	10	10	10	10	10
Serum chemistry b,c	10		10	10	10	10	10	10				10
CBC, differential, platelets e	7		7	7	7	7	7	7				7
PT (INR), PTT e	5		5			5						5
Serum IgA	7											
SYN023 Pharmacokinetics e			14	7	7	7	7	7	7	7	7	
Anti-SYN023 antibodies e			5			5	5	5	5	5	5	5
Weight	X		X									X
Vital signs & oximetry	X		X	X	X	X	X	X				X
Interval history			X	X	X	X	X	X	X	X	X	X
Focused physical examination			X	X	X	X	X	X	X	X	X	X
Solicited adverse events (incl. con. meds.)			X	X	X	X	X	X				
Unsolicited adverse events (incl. con. meds.)			X	X	X	X	X	X	X	X		
Serious adverse events (incl. con. meds.)			X	X	X	X	X	X	X	X	X	X
Site of injection examination			X	X	X	X	X	X	X	X		X
Lymphadenopathy			X	X	X	X	X	X	X	X		X
Per visit phlebotomy volume	35	5	51	34	34	39	39	39	22	22	22	37
Cumulative phlebotomy volume e	35	40	91	125	159	198	237	276	298	310	332	369

- Results must be known before Study Drug administration
- Serum Chemistry: creatinine phosphokinase (CPK), troponin, total bilirubin, AST, ALT, ALP, creatinine, blood urea nitrogen, sodium, potassium, chloride, bicarbonate, calcium. Note minimum serum chemistry labs for screening visit are: AST, ALT, ALP and creatinine although other labs monitored for safety may be collected if part of panel.
- The cumulative phlebotomy volume is approximate.
- Visit window refers to acceptable variation in days either early or late from scheduled visits in without a protocol violation.
- Must be obtained on day of visit but prior to any injections.

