### **3.2.5 Screening Clinical Assessments and Laboratory Tests**

Unless noted otherwise, the window period within which all screening evaluations must be completed, and the results reviewed by the investigator to confirm eligibility of subjects, is 28 days prior to Study Day 0.

Subjects will provide a detailed medical history and subjects will undergo a physical examination. The assessment will include the determination of any surgeries or medically significant procedures planned to occur during the entire study period. Demographic characteristics (date of birth, gender, and race/ethnicity) will also be collected. Any new abnormal findings will be discussed with the subject and referral will be made for follow-up care if necessary.

Screening laboratory tests (See Table 3.1-1) will be performed during the screening process. Results from some of these laboratory tests (HIV, Hepatitis B and C, serum IgA) may serve as study-entry baseline values if not required for Study Day 0. Values from specimens obtained at on or after Study Day -2 will not be required to be redrawn prior to study start on Study Day 0 and the values will serve as baseline values. Eligibility is determined by screening laboratory

tests. All laboratory tests for Study Day 0 must be drawn prior to study drug administration. Abnormal results and findings that make the subject ineligible will be discussed with the subject and the subject will be referred for follow-up care with their healthcare provider if necessary. All screening laboratory specimens will be processed according to laboratory SOPs available from the clinical laboratory(ies) designated for the study. Information about the laboratory(ies), including any instructions for performing and interpreting specific tests, will be maintained in the investigator's study files.

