**APPENDIX A Detailed Description of Selected Study Visits****Screening Visit (Up to 4 weeks prior to start of study medication, Day -28 to -1)**

- Obtain informed consent
- Verify eligibility by review of inclusion/exclusion criteria
- Record medical history
- Conduct physical examination (including height and weight and BMI calculation)
- Perform ECG
- Collect urine sample for:
  - $\beta$ HCG (all females)
  - Urinalysis
  - Urine Toxicology
- Collect blood samples for:
  - Hepatitis B, Hepatitis C, HIV-1,2
  - PT and PTT
  - Serum chemistry: creatinine, ALT, AST, alkaline phosphatase and others if part of panel
  - Hematology: CBC including differential and platelets
  - Serum IgA

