Calcium – hypocalcemia mg/dL: mmol/L:	8.0 – 8.4 2.00 – 2.10	7.5 – 7.9 1.87 – 1.99	7.0 – 7.4 1.75 – 1.86	<7.0 <1.75
Calcium – hypercalcemia mg/dL: mmol/L:	10.5 – 11.0 2.63 – 2.76	11.1 – 11.5 2.77 – 2.88	11.6 – 12.0 2.89 – 3.00	>12.0 >3.00
Magnesium – hypomagnesemia mg/dL: mmol/L:	1.3 – 1.5 0.52 – 0.62	1.1 – 1.2 0.43 – 0.51	0.9 – 1.0 0.37 – 0.42	<0.9 <0.37
Phosphorus – hypophosphatemia mg/dL: mmol/L:	2.3 – 2.5 0.73 – 0.80	2.0 – 2.2 0.63 – 0.72	1.6 – 1.9 0.51 – 0.62	<1.6 <0.51
CPK – elevated mg/dL or ukat/L:	1.25 – 1.5 x ULN***	1.6 – 3.0 x ULN	3.1 – 10 x ULN	>10 x ULN
Albumin – hypoalbuminemia g/dL: g/L:	2.8 – 3.1 28 – 31	2.5 – 2.7 25 – 27	<2.5 <25	---- ----
Total protein – hypoproteinemia g/dL: g/L:	5.5 – 6.0 55 – 60	5.0 – 5.4 50 – 54	<5.0 <50	---- ----
Alkaline phosphatase (ALP) – increased	1.1 – 2.0 x ULN	2.1 – 3.0 x ULN	3.1 – 10 x ULN	>10 x ULN
Liver Function Tests (LFT): AST, ALT – increased	1.1 – 2.5 x ULN	2.6 – 5.0 x ULN	5.1 – 10 x ULN	>10 x ULN
Bilirubin (with any increase in LFT) - increased	1.1 – 1.25 x ULN	1.26 – 1.5 x ULN	1.51 – 1.75 x ULN	>1.75 x ULN
Bilirubin (with normal LFT) - increased	1.1 – 1.5 x ULN	1.6 – 2.0 x ULN	2.1 – 3.0 – x ULN	>3.0 x ULN

Cholesterol – increased mg/dL: mmol/L:	201 - 210 6.0 – 6.3	211 – 225 6.4 – 6.7	>226 >6.7	---- ----
Pancreatic enzymes: amylase, lipase – increased	1.1 – 1.5 x ULN	1.6 – 2.0 x ULN	2.1 – 5.0 x ULN	>5.0 x ULN

6. \*\* The clinical signs or symptoms associated with laboratory abnormalities might result in characterization of the laboratory abnormalities as Very Severe (Grade 4). For example, a low sodium value that falls within a grade 3 parameter (125-129 mEq/L) should be recorded as a Grade 4 hyponatremia event if the subject had a new seizure associated with the low sodium value.
7. \*\*\* ULN (upper limit of normal) dependent on normal reference ranges per institutional parameters.

Hematology	Mild (Grade 1)	Moderate (Grade 2)	Severe (Grade 3)	Very Severe (Grade 4)
Hemoglobin (Female) – g/dL: g/L:	11.0 – 12.0 110 – 120	9.5 – 10.9 95 – 109	8.0 – 9.4 80 – 94	<8.0 <80
Hemoglobin (Male) – g/dL: g/L:	12.5 – 13.5 125 – 135	10.5 – 12.4 105 – 124	8.5 – 10.4 85 – 104	<8.5 <85
WBC – increased cells/mm  : cells x 10  /L:	10,800 – 15,000 10.8 – 15.0	15,001 – 20,000 15.1 – 20.0	20,001 – 25,000 20.1 – 25.0	>25,000 >25.0
WBC – decreased cells/mm  : cells x 10  /L:	2,500 – 3,500 2.5 – 3.5	1,500 – 2,499 1.5 – 2.4	1,000 – 1,499 1.0 – 1.4	<1,000 <1.0

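### Exclusion 3 lets one of AST, ALT or ALP exceed the ULN by more than 10% and sets no upper limit, so an isolated Grade 3 or 4 value meets the exception

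*Protocol*

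**What the plan says.** Protocol 3.2.4, exclusion 3, has two parts. The base rule excludes anyone with "Abnormally elevated aspartate aminotransferase (AST), alanine aminotransferase (ALT), total bilirubin, alkaline phosphatase (ALP), or creatinine (Cr) values at screening". A parenthesis then relaxes it: "however a single test AST, ALT or ALP may be" more than 10% above the ULN by the local laboratory's range. The printed sign is a greater-than sign. What counts as abnormally elevated is not defined.

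Exclusion 2, just above it, uses a percentage in the opposite role. "Complete blood count (CBC) and platelet count abnormal values" are disqualifying when they lie more than 5% outside the normal limits.

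Appendix E grades these enzymes in multiples of the ULN. The row "Liver Function Tests (LFT): AST, ALT – increased" starts Grade 1 at 1.1, and the ALP row starts at the same point.

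On total bilirubin the protocol gives two answers. Exclusion 3 names it. Section 3.2.2 puts it among the chemistry values that "are not part of the inclusion/exclusion criteria as such". The screening panel does not require it either. Table 3.1-1 says "Note minimum serum chemistry labs for screening visit are: AST, ALT, ALP and creatinine", and Appendix A lists "Serum chemistry: creatinine, ALT, AST, alkaline phosphatase and others if part of panel" for the screening visit.

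**The concern.** A clause saying that a value may exceed a threshold sets a floor for the exception. A tolerance for a small isolated enzyme rise needs a ceiling, and none is printed. Exclusion 3 is the only numeric liver-enzyme criterion in the protocol, and 3.2.2 makes AST, ALT and ALP, with creatinine, the screening chemistry that decides entry.

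At stake is the protection of healthy adults who receive an investigational antibody or immune globulin plus five vaccine doses. As printed, a volunteer with one markedly raised enzyme meets the written criterion. Keeping that person out then depends on other provisions that contain no enzyme value. Sites and monitors also have no number against which to call such an enrolment a deviation.

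The bilirubin conflict is a separate and smaller point with the same practical effect: a site cannot comply with both texts.

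**Working it through.** The plan gives no figure to reproduce. The check sets the printed limit against the Appendix E grades and then looks for a ceiling elsewhere.

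**Inputs**

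- Printed exception (3.2.4, exclusion 3): one of AST, ALT or ALP may be above 1.10 x ULN.
- AST/ALT grades (Appendix E): Grade 1 is 1.1–2.5, Grade 2 is 2.6–5.0, Grade 3 is 5.1–10, Grade 4 is above 10 x ULN.
- ALP grades (Appendix E): Grade 1 is 1.1–2.0, Grade 2 is 2.1–3.0, Grade 3 is 3.1–10, Grade 4 is above 10 x ULN.

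**Formula:** percent above ULN = (multiple of ULN − 1) x 100.

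- (1.05 − 1) x 100 = 5%
- (3.1 − 1) x 100 = 210%
- (5.1 − 1) x 100 = 410%
- (10.1 − 1) x 100 = 910%

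**Two readings of the printed text.** The base term is undefined, so both are applied. Each row assumes that all other exclusion 3 tests are normal.

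- Reading A: abnormally elevated means above the ULN, and the exception covers one test above 1.10 x ULN.
- Reading B: abnormally elevated itself means more than 10% above the ULN, and one test may exceed that threshold.

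The last column shows the rule with a limit of not more than 10% above the ULN.

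| Isolated value | Above ULN | Grade | Reading A | Reading B | Limit of 1.10 x ULN |
|---|---|---|---|---|---|
| AST/ALT 1.05 x ULN | 5% | none | excluded | allowed | allowed |
| AST/ALT 5.1 x ULN | 410% | 3 | allowed | allowed | excluded |
| AST/ALT 10.1 x ULN | 910% | 4 | allowed | allowed | excluded |
| ALP 1.05 x ULN | 5% | none | excluded | allowed | allowed |
| ALP 3.1 x ULN | 210% | 3 | allowed | allowed | excluded |
| ALP 10.1 x ULN | 910% | 4 | allowed | allowed | excluded |

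The Grade 3 and 4 rows come out the same under both readings. The 1.05 x ULN rows do not, so no conclusion is drawn from them.

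**Search for a ceiling elsewhere**

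- 3.2.2, 3.2.5, Table 3.1-1 and the Appendix A screening visit name the tests and their timing but give no enzyme limit.
- Exclusion 9 covers chronic hepatitis, and exclusion 11 covers other disease that the investigator judges relevant. Neither gives a value.
- Appendix E grades events. It is not an entry criterion.
- Chemistry is repeated on Day 0, except that specimens from Day −2 onward "will not be required to be redrawn prior to study start on Study Day 0". The repeat serves as a baseline, and no entry limit is attached to it.

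**Total bilirubin.** Exclusion 3 makes it an eligibility test. Section 3.2.2 says that it is not one, and Table 3.1-1 and Appendix A leave it optional at screening. A site that runs only the minimum panel cannot apply exclusion 3 in full.

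**The case against.** The strongest reply is that the clause makes sense as written. On Reading B, 10% above the ULN is the abnormality threshold, and the sponsor chose to let one enzyme exceed it. Exclusion 2 uses a threshold of the same form, and Grade 1 starts at 1.1 x ULN, so both fit this reading as well as they fit a reversed sign. That stands against any claim of a proven typing error. It does not supply a ceiling.

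A reader might infer that the rule runs backwards, turning away 1.05 x ULN while accepting 10 x ULN. That holds only on Reading A. The documents do not define the term, so they do not support it as a general statement.

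A reader might also infer that only the investigator's judgment stands in the way. That goes too far. Hepatitis B and C serology is done at screening, and exclusion 9 carries no opinion qualifier. Two abnormally elevated enzymes, or a raised creatinine, still exclude. Exclusion 11 names hepatic disease, and under 5.1.1 the principal investigator may delay an individual's dosing. These provisions narrow practical exposure, but none sets an enzyme limit.

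Finally, the point turns on one character in text converted from PDF. Inequality signs in neighbouring exclusions came through plausibly, so a misread is possible rather than likely. The original page should be checked.

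**Conclusion.** The concern holds for the missing ceiling. As printed, an isolated AST or ALT of at least 5.1 x ULN, or an isolated ALP of at least 3.1 x ULN, meets the exception under either reading. This rests on the greater-than sign being what the original page shows, and on the other exclusion 3 tests being normal. A limit of not more than 10% was probably intended, but that is an inference.

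Meeting the exception is not the same as being enrolled. The documents give no basis for estimating how often such volunteers would appear, and a careful investigator would probably exclude them.

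A reader might infer that a high entry value would hide later liver signals. The documents do not support that. Protocol 5.3 counts worsening of a baseline condition as an adverse event. SAP 9.3 takes the last result before the first vaccine dose as baseline and reports change from baseline and shifts. The primary RVNA analysis is not touched.

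The bilirubin inconsistency is real and independent of how the sign is read. Both points are worth correcting because the criterion protects healthy volunteers and the correction is short.

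**What to change.** 1. Check the sign in exclusion 3 against the original page.
2. State that abnormally elevated means above the ULN, and reword the exception: *a single AST, ALT or ALP may be above the ULN but not more than 10% above it*. The exception then ends where Grade 1 begins, and no Grade 2, 3 or 4 value can meet it.
3. If a wider tolerance was meant, state the ceiling. The top of Grade 1 is one option (2.5 x ULN for AST/ALT, 2.0 x ULN for ALP). The documents do not point to a particular value, so the choice is the sponsor's.
4. Settle total bilirubin. Either keep it in exclusion 3, add it to the minimum screening panel in Table 3.1-1 and Appendix A and correct 3.2.2, or delete it from exclusion 3.

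The cost is a one-sentence eligibility amendment plus the bilirubin alignment. Under Protocol section 12 it needs sponsor approval, and IRB/IEC approval before use. Screen failures may change slightly, in a direction that depends on how sites apply the clause now. Endpoints, sample size and analyses do not change.

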### **3.2.5 Screening Clinical Assessments and Laboratory Tests**

Unless noted otherwise, the window period within which all screening evaluations must be completed, and the results reviewed by the investigator to confirm eligibility of subjects, is 28 days prior to Study Day 0.

Subjects will provide a detailed medical history and subjects will undergo a physical examination. The assessment will include the determination of any surgeries or medically significant procedures planned to occur during the entire study period. Demographic characteristics (date of birth, gender, and race/ethnicity) will also be collected. Any new abnormal findings will be discussed with the subject and referral will be made for follow-up care if necessary.

Screening laboratory tests (See Table 3.1-1) will be performed during the screening process. Results from some of these laboratory tests (HIV, Hepatitis B and C, serum IgA) may serve as study-entry baseline values if not required for Study Day 0. Values from specimens obtained at on or after Study Day -2 will not be required to be redrawn prior to study start on Study Day 0 and the values will serve as baseline values. Eligibility is determined by screening laboratory

tests. All laboratory tests for Study Day 0 must be drawn prior to study drug administration. Abnormal results and findings that make the subject ineligible will be discussed with the subject and the subject will be referred for follow-up care with their healthcare provider if necessary. All screening laboratory specimens will be processed according to laboratory SOPs available from the clinical laboratory(ies) designated for the study. Information about the laboratory(ies), including any instructions for performing and interpreting specific tests, will be maintained in the investigator's study files.

### **3.2.5.1 Window Period for Select Screening Laboratory Tests**

Select laboratory evaluations must be performed on specimens obtained within two days (Study Day -2) prior to study entry on Study Day 0, and the results must be known and eligibility confirmed prior to study entry on Study Day 0. Screening tests that must be obtained  $\leq 48$  hours prior to receipt of SYN023 or RIG on Study Day 0 include the following: serum  $\beta$ HCG for women only. The results from tests performed on specimens collected within 48 hours prior to study entry on Study Day 0 may serve as both screening and Study Day 0 evaluations.

If blood specimens for serum anti-rabies activity, SYN023 pharmacokinetics (pre dose) and anti-SYN023 antibodies are also taken within two days prior to study entry on Study Day 0, these specimens may be used as the Study Day 0 evaluations for subjects who subsequently are randomized.

## **3.3 Study Randomization and Sentinel Subjects**

Subjects will be randomized to the study based on a randomly-generated sequence of subject identification numbers (randomization schedule). The randomization schedule will be prepared by a statistician who will not be involved in the analysis of the study in order to maintain the blind of the study team. A subject is considered randomized when a subject identification number has been assigned to them on Study Day 0. The first four subjects entered into the study (sentinel subjects) will be randomized such that a subject each receives one of the four possible regimens. Safety information on these sentinel subjects through study day 14 will be collected and reviewed by the medical monitor and principal investigator before the remainder of the trial is enrolled.

Subjects who withdraw from the study or are discontinued may be replaced by modification of the remaining randomization schedule. Unless there is reason to pause the study, based on the study pausing rules as outlined in Section 6.1, then the principal investigators may proceed to enroll all of the subjects.

